7.2 Randomisation, blinding and treatment allocation

Subjects after cardiac arrest and successful cardiopulmonary resuscitation that are admitted to an intensive care unit of a participating hospital can be considered for enrolment in the study. Randomisation will be 1:1, in blocks of N=10, stratified by study site. Randomisation will be performed if the subject meets all inclusion/exclusion criteria and will be processed centrally by means of a web-based system that will provide the randomisation treatment arm (Ghrelin or placebo). The online system (Research Manager®), is constructed and validated for randomization and data management and has an audit trail. Contact persons of all participating centres can sign in and randomize their patients.

A legal representative or family member will be informed and patients will be included on the intensive care by their treating intensive care physician. Once informed consent is obtained, the collaborating hospital pharmacist will be notified by the intensive care physician. The pharmacist will sign in Research Manager, include the patient and randomize. The pharmacist will receive the treatment allocation through Research Manager, and thus be unblinded. He / she will prepare the treatment or placebo and provide it to the treating intensive care physician. The intensive care physician will remain blinded to the treatment allocation.

The investigator can decide to withdraw a subject from the study for urgent medical reasons. In this case the investigator can decide to 'unblind' the patient. For unblinding, the unblinded collaborating pharmacist will provide information on the treatment allocation to the treating intensive care physician.

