7.7 Premature termination of the study

Planned interim analyses will be performed after 1, 2, 3, 4, 5, 6, 7, 8, 9, 10, 15, 20, 25, 50, and 100 inclusions. The interim analyses will only be directed at safety. The trial will be stopped because of any safety issue of the treatment under study, defined as a higher occurrence of SAEs in the treatment than in the control group. There will be no interim analysis for efficacy in this trial, since it is very unlikely that either 'futility' or 'proof beyond reasonable doubt' will be achieved prematurely in this relatively small phase 2 clinical trial.

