8.4 Follow-up of adverse events

All AEs will be followed until they have abated, or until a stable situation has been reached. Depending on the event, follow up may require additional tests or medical procedures as indicated, and/or referral to the general physician or a medical specialist.

SAEs need to be reported till end of study within the Netherlands, as defined in the protocol.

8.5 [Data Safety Monitoring Board (DSMB) / Safety Committee]

The trial will be monitored by an independent data monitoring committee. The data monitoring board (DSMB) will consist of Dr. [name] (neurologist UMCU), [name] (intensivist UMCU), Dr. [name] (biostatistician LUMC), and dr. [name] (clinical pharmacologist Apotheek Haagse Ziekenhuizen en Hagaziekenhuis). The first three members of this DSMB are also involved in the TELSTAR trial (www.telstartrial.nl) and know the vulnerable population under study very well. Details on the DSMB and rules on analysis and reporting are included in K5: “DSMB charter”.

The DSMB is established to perform interim analyses for safety. Safety analyses will be performed at an individual patient level for the first ten inclusions in the trial. For these first ten inclusions, the DSMB will receive by email unblinded reports of SAEs, AEs, SUSARs, poor outcomes, and deaths after each individual inclusion. Thereby, the DSMB will have access to individual patient files. The information will be sent to the DSMB at one week \pm 3 days after inclusion (i.e. the duration of treatment). Analysis of safety in these first ten inclusions will be largely qualitative. The first ten patients will be included sequentially in one hospital (MST), where the next inclusion will only take place after a positive sign from the DSMB.

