Thereafter, the DSMB will perform safety analyses after 15, 20, 25, 50, and 100 inclusions. At that time, the DSMB will review data on SAEs, SUSARs, poor outcomes, and deaths per centre. This information will be sent to the DSMB at one week \pm 3 days after inclusion for the interim analyses at 15, 20, and 25 inclusions. For these interim analysis, the trial will only continue after a positive sign from the DSMB. For the interim analyses at 50 and 100 inclusions, the information will be sent after having reached the secondary outcome measure at three months. In addition, the DSMB will review general aspects of the trial, including patient recruitment, patient inclusion, and unexpected events. Because of the expected high proportion of patients with a poor outcome in the patient group under study, and the consequent overlap between safety endpoints and the primary endpoint, the evaluation of safety by the DSMB will be quantitative and qualitative. In addition, suspected unexpected serious adverse reactions (SUSARs) will be reported <48 hours to the METC.

The composition, tasks and responsibilities of the DSMB are described in K5: DSMB Charter.

The DSMB will advise to stop the trial at the following moments:

- A higher number of SAEs in the treatment than in the control group
- Any SUSARs
- Any other safety issues

The advice(s) of the DSMB will be sent to the Principle Investigator of the study and the METC. Should the Principle Investigator decide not to fully implement the advice of the DSMB, the Principle Investigator will send the advice to the reviewing METC, including a note to substantiate why (part of) the advice of the DSMB will not be followed.

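### The SAE count rule in 7.7 and 9.4 is not reconciled with the qualitative review of the first ten patients in 8.5; followed literally, a go signal shows that the first SAE patient was on placebo

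*Protocol*

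**What the plan says.** **Looks.** Section 7.7: "Planned interim analyses will be performed after 1, 2, 3, 4, 5, 6, 7, 8, 9, 10", followed by further looks up to 100 inclusions.

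**Stop rule.** The same section stops the trial for a safety issue, "defined as a higher occurrence of SAEs in the treatment than in the control group". No margin, minimum count or exempt look is given. Section 9.4 repeats the rule and adds any SUSAR or other safety concern. Section 8.5 lists the same comparison among the reasons for the DSMB to advise stopping: "A higher number of SAEs in the treatment than in the control group".

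**First ten patients.** Under 8.5, "the DSMB will receive by email unblinded reports of SAEs, AEs, SUSARs, poor outcomes, and deaths after each individual inclusion". These patients come from a single hospital, and "the next inclusion will only take place after a positive sign from the DSMB". The same paragraph adds: "Analysis of safety in these first ten inclusions will be largely qualitative".

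**Who knows what.** Section 7.2 keeps the treating intensive care physician blinded and states the scheme: "Randomisation will be 1:1, in blocks of N=10, stratified by study site". Section 8.2.1 has a study nurse discuss all AEs and SAEs with the principal investigator every week. Section 8.5 says: "The advice(s) of the DSMB will be sent to the Principle Investigator of the study and the METC".

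**The concern.** The hospital knows which of its patients had an SAE and in what order. It can read the stop rule in the protocol, and it learns after each patient whether inclusion may go on. If the rule is what decides that signal, the signal carries information about allocation to people whom 7.2 keeps blinded. The principal investigator is in the same position, receiving both the SAE reports and the DSMB advice.

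At stake are the blinded reporting of later adverse events at that hospital and, possibly, the estimated CPC at one week. The issue also continues past patient ten. Section 8.5 requires a positive sign at 15, 20 and 25 inclusions and there calls the evaluation both quantitative and qualitative. Under the published rule, each permission to continue tells investigators that ghrelin has no more SAEs than control. Death is listed as an SAE in 8.2.2, and 8.5 itself notes that safety endpoints overlap with the primary endpoint.

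**Working it through.** **The plan's own figures.** The protocol gives no figure for the stop rule or for unblinding. Its sample size serves here only as a denominator, and it reproduces: 2 × (1.960 + 0.842)² × 1.8² / 0.8² ≈ 79.5, so 80 per arm and 160 in total.

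**Inputs**
- Ten looks, one after each patient (7.7, 8.5).
- Stop if SAE patients on ghrelin outnumber those on control (7.7, 8.5, 9.4).
- One block of ten at one site, hence 5:5 (7.2), giving C(10,5) = 252 allocations.
- Assumed: the rule is followed exactly, each patient has at most one counted SAE, and the SAE risk *p* is equal in both arms.
- The value of *p* is not stated. Section 8.2.1 gives a case fatality of 50–60%, with most deaths in the first week, and SAEs include more than deaths. Against that, 8.2.4 treats deaths more likely due to disease progression as expected AEs. A range of 0.25 to 0.60 is therefore shown.

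**Step 1: the first SAE.** If it occurs on ghrelin, the count is 1 v 0 and the rule stops the trial. If it occurs on placebo, the count is 0 v 1 and the trial continues. Hence P(placebo | continue) = 1. Conversely, a stop on the SAE count would place the latest SAE patient on ghrelin.

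**Step 2: later SAEs.** With one placebo SAE recorded, a second SAE passes in either arm (1 v 1 or 0 v 2). Suppose patients 1 and 2 have SAEs and nobody else does. The consistent allocations are those with patient 1 on placebo, 252/2 = 126. In C(8,3) = 56 of them patient 2 is also on placebo, so P(placebo) = 56/126 = 0.44. That is close to a coin toss, and the departure from 0.50 comes from the block alone. If the first six patients all have SAEs, the six probabilities of placebo are 1.00, 0.65, 0.65, 0.51, 0.51 and 0.34.

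**Step 3: patients without an SAE.** The count does not change, so under the count rule the signal after such a patient adds nothing new.

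**Step 4: all patterns.** For each of the 2¹⁰ = 1,024 SAE patterns, the allocations that pass all ten looks were kept. Each pattern was weighted by p^k (1 − p)^(10 − k), with k the number of SAE patients, times the fraction of the 252 allocations that pass. An SAE patient is certain if all consistent allocations agree on the arm. The best guess is correct with probability max(q, 1 − q), where q is the probability of placebo.

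| SAE risk | Runs passing all ten looks | Mean SAE patients in those runs | Mean number certain | Share of SAE patients certain | Mean correct guess |
|---|---|---|---|---|---|
| 0.25 | 45.6% | 2.13 | 0.88 | 41% | 76% |
| 0.30 | 41.6% | 2.64 | 0.93 | 35% | 74% |
| 0.40 | 35.5% | 3.65 | 0.98 | 27% | 70% |
| 0.50 | 30.9% | 4.67 | 1.00 | 21% | 68% |
| 0.55 | 28.9% | 5.18 | 1.00 | 19% | 67% |
| 0.60 | 27.1% | 5.69 | 1.00 | 18% | 67% |

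The columns from the third onward are conditional on passing all ten looks. The certain patient is almost always the first with an SAE. SAE patients after the first are guessed correctly about 60% of the time throughout. Simple 1:1 randomisation gives nearly the same certain share (21%, 19% and 17% at risks 0.50, 0.55 and 0.60), so the leak does not depend on the block.

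**Step 5: a DSMB that does not apply the rule mechanically.** Suppose, for illustration, that it lets a first ghrelin SAE pass with probability 0.3. At that look P(placebo | continue) = 0.5 / (0.5 + 0.5 × 0.3) = 0.77. Information still leaks, but certainty is gone.

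**The case against.** A reader might infer that every positive sign reveals an arm, or that the blind fails in the first ten patients. The working does not support either. A sign after a patient without an SAE adds nothing, and after the first SAE the later signs only shift probabilities. About one patient in ten is identified, and 1/160 = 0.6% of the planned trial.

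The strongest defence is that 8.5 rules out a mechanical decision for exactly these patients: review is individual, with access to patient files, and is described as mainly qualitative. The principal investigator may depart from the advice with a note to the METC, and the detailed rules sit in a charter that is not shown. This removes certainty, as step 5 shows. It does not dispose of the point, because 7.7 and 9.4 state the count rule without exempting these looks, and 8.5 itself repeats it as a ground for advising a stop. Either the rule binds and the signal leaks, or it does not bind and the sections disagree.

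Three further objections stand in part:
- The figures apply only to runs that pass all ten looks. In the other 54% to 73% the literal rule stops the trial even with a harmless drug. That is a larger defect of the same rule and a separate point.
- The DSMB receives its data about one week after inclusion, around the end of treatment. Section 7.3 assigns the three- and six-month CPC to a trained research nurse by telephone, and a death cannot be rescored by someone who later learns the arm. Bias in the primary outcome is therefore unlikely to be material.
- A go signal after an SAE can carry some information under qualitative review too. No wording removes that entirely.

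**Conclusion.** The point holds as a contradiction with a limited leak. Sections 7.7 and 9.4 and the advice list in 8.5 do not fit the mainly qualitative review that 8.5 prescribes for the first ten patients. Read literally, they identify the first SAE patient as placebo to staff meant to stay blinded, and they partly unblind later SAE patients: 0.9 to 1.0 patients certain per run that passes all ten looks, over SAE risks of 0.25 to 0.60.

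This rests on the rule being followed exactly, at most one counted SAE per patient and equal risk by arm. With several SAEs per patient, the first SAE patient is still revealed but the later probabilities change. The documents do not support a claim that the blind is lost for the ten patients as a group, or that the six-month comparison is compromised. The reason to act is that the protocol gives two incompatible accounts of how looks 1 to 10 are decided, and one of them exposes allocation unnecessarily.

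**What to change.** Reconcile 7.7, 9.4 and the advice list in 8.5 with the qualitative review of the first ten patients. State that at looks 1 to 10 the between-arm SAE count does not by itself determine the go signal. For all looks, refer any numerical between-arm comparison to the closed part of the DSMB charter, so that permission to continue does not tell investigators how the arms compare.

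This changes only protocol and charter wording; the DSMB's access to unblinded data and its individual review are unaffected. The cost is some transparency, because investigators would no longer see the numerical trigger.

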9. STATISTICAL ANALYSIS

9.1 Primary study parameter(s)

The primary analysis will be a single comparison between the treatment groups of the primary outcome measure after six months. This analysis will be performed according to the intention-to-treat principle. To assess the effect of treatment with ghrelin, the whole range of the CPC will be taken into account. This indicates that no dichotomy will be used in the primary analysis. Instead of a dichotomy, any shift in the direction of a better

outcome on de CPC scale will be analyzed. This will be expressed as a common odds ratio for improvement.²⁷

9.2 Secondary study parameter(s)

With regard to the range of secondary outcome parameters, we will use simple 2x2 tables, two-group t-tests, Mann-Whitney tests, or multivariable linear and logistic regression models, where appropriate. In all analyses, statistical uncertainty will be quantified by means of 95% confidence intervals. Subgroup analyses based on the EEG pattern at 24 hours will be carried out for the following subgroups: (1) suppressed patterns and suppressed patterns with synchronized periodic activity, (2) continuous patterns, and (3) other patterns. This is based on our previous studies on EEG based outcome prediction of comatose patients after cardiac arrest, where the first subgroup represents patterns that are strongly associated with a poor prognosis, the second subgroup with a good prognosis, and the third subgroup with an intermediate prognosis.[refs] Although the size of this study will not allow for precise estimates of treatment effect in subgroups, we will assess heterogeneity of effects, and analyze consistency of effects on secondary outcomes.

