4. STUDY POPULATION

4.1 Population (base)

Comatose patients (GCS score of 8 or lower) after cardiac arrest and successful cardiopulmonary resuscitation, admitted to intensive care units of participating hospitals, will be included within 12 hours after return of spontaneous circulation. Informed consent and randomization will have to be obtained within 12 hours after return of spontaneous circulation. The trial treatment will have to be started within three hours after randomization (please see procedure at 7.3).

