7.1.3 Other study parameters

We assume that potential effects of ghrelin are mediated by mild neuronal activation, preventing ill-fated neuronal inactivity. This is based on studies under experimental in vitro and in vivo conditions.^{10,18} To study effects of ghrelin on neuronal activity, we consider brain activity as measured by the EEG. Continuous EEG measurements during day 0-3 after

cardiac arrest are performed in all participating hospitals in the context of current care. The following EEG measures will be extracted and studied in relation to ghrelin treatment: the temporal brain symmetry index (tBSI),²⁴ the cerebral recovery index (CRI)²⁵ and EEG background continuity.²⁶ All three measures strongly represent restoration of brain activity after an hypoxic insult and are strongly related to clinical recovery.

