7.3 Study procedures

All comatose patients after cardiac arrest will be admitted to intensive care units to receive treatment according to guidelines, as described in national and local ICU protocols.

A legal representative or family member of all eligible patients will be informed about the study as soon as possible after admission on the ICU by the ICU staff/research coordinators. Since any beneficial effect of the treatment under study is assumed to be larger with earlier

initiation, randomization and treatment should be initiated within 12 hours after cardiac arrest (ROSC). All participating centers have ample experience with inclusion of patients with acute cardiac arrest or cerebral ischemia in intervention studies.

Patients who are enrolled in this trial will receive intravenous treatment with acylated ghrelin 600micrg twice daily vs. placebo. The duration of the treatment is one week. This treatment duration of one week will be adhered to, both in patients that remain comatose, and in patients that awaken within a week. If patients are transferred from the ICU to a cardiac care unit or general ward within one week, treatment will be continued for a total of one week, as well. Intravenous treatment will be administered through infusion systems that are already in situ in all of these patients. There will be no additional punctures.

Baseline data will be obtained at admission as part of regular patient care and include: clinical data, EEG data, medical history, and use of medication. In addition, a venous blood samples (5cc) will be taken to measure the baseline ghrelin concentration. This sample will be collected during routine blood sampling; there will be no additional punctures.

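### The EEG subgroups are formed at 24 hours, after dosing has begun, on a feature that the protocol studies as a response to ghrelin; if ghrelin shifts that feature, the subgroup effects are biased

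*Protocol*

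**What the plan says.** Protocol section 9.2 fixes the subgroup variable and its time: "Subgroup analyses based on the EEG pattern at 24 hours will be carried out for the following subgroups". There are three classes: suppressed patterns (with or without synchronised periodic activity), continuous patterns, and all others. They are chosen because earlier work linked them to poor, good and intermediate prognosis. The section says heterogeneity of effects will be assessed. Its only caution is that subgroup estimates will be imprecise.

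On timing, section 4.1 says: "Informed consent and randomization will have to be obtained within 12 hours after return of spontaneous circulation". It adds: "The trial treatment will have to be started within three hours after randomization". Sections 7.3 and 10.2 instead want treatment itself begun within 12 hours of the arrest. Section 7.3 gives the regimen as "intravenous treatment with acylated ghrelin 600micrg twice daily vs. placebo".

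On mechanism, section 7.1.3 says: "We assume that potential effects of ghrelin are mediated by mild neuronal activation, preventing ill-fated neuronal inactivity". It continues: "To study effects of ghrelin on neuronal activity, we consider brain activity as measured by the EEG". Background continuity is one of three EEG measures to be related to ghrelin treatment, and all three are described as strongly related to recovery.

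On earlier EEG data, section 7.3 says: "Baseline data will be obtained at admission as part of regular patient care and include: clinical data, EEG data".

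**The concern.** A subgroup analysis of a randomised trial keeps the protection of randomisation only if treatment cannot influence who falls into which subgroup. Here the sorting variable is read after treatment has started, and it is close to the feature that the drug is meant to change. The protocol uses that feature both as a response to ghrelin and as a prognostic stratum.

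If ghrelin does move patients between classes, the ghrelin and placebo patients in one class are different kinds of patient. The ghrelin patients with a continuous EEG would include some who would have had a worse pattern on placebo. The contrast within the class then mixes the drug effect with a change in case mix. The bias can hide benefit or suggest harm, and a larger sample does not shrink it. What is at stake is the reading of the subgroup effects and of their heterogeneity.

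**Working it through.** **Timing.** Counting 24 hours from return of circulation:
- start by 12 h (sections 7.3 and 10.2): 24 − 12 = at least 12 h after the first dose;
- randomisation by 12 h plus 3 h (section 4.1), so start by 15 h: 24 − 15 = at least 9 h after the first dose.

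Section 9.2 does not say what the 24 hours are counted from. If they run from randomisation, the gap is at least 24 − 3 = 21 h. At least one dose has been given under each reading; whether a second has depends on a dosing interval that is not stated. The two limits on treatment start need to be reconciled, but the point holds under either.

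**Size.** The protocol gives no figure for this analysis, so there is none to reproduce. The sample size of 160 is not in question. The following illustration rests on assumptions that are not in the documents:
- placebo shares suppressed / other / continuous: 0.25 / 0.45 / 0.30;
- good-outcome rates: 0.05 / 0.45 / 0.90, so overall 0.0125 + 0.2025 + 0.27 = 0.485;
- ghrelin moves a fraction f of each of the two lower classes up one class, and those moved are typical of the class they leave.

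At f = 0.2 the ghrelin shares become:
- suppressed: 0.25 × 0.8 = 0.20;
- other: 0.45 × 0.8 + 0.25 × 0.2 = 0.41;
- continuous: 0.30 + 0.45 × 0.2 = 0.39.

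*(a) The EEG changes but the outcome does not (true odds ratio 1.0).* Those moved keep the rate of the class they left.
- Other: (0.36 × 0.45 + 0.05 × 0.05) / 0.41 = 0.401. Odds ratio (0.401/0.599) / (0.45/0.55) = 0.82.
- Continuous: (0.30 × 0.90 + 0.09 × 0.45) / 0.39 = 0.796. Odds ratio (0.796/0.204) / (0.90/0.10) = 0.43.

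*(b) The benefit is carried entirely by class changes.* Those moved take the rate of the class they enter.
- Overall: 0.20 × 0.05 + 0.41 × 0.45 + 0.39 × 0.90 = 0.5455. Odds ratio (0.5455/0.4545) / (0.485/0.515) = 1.27.
- Within each class the rates equal those on placebo, so every odds ratio is 1.0.

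| f | (a) odds ratio in continuous | (b) true overall odds ratio | (b) odds ratio in each class |
|---|---|---|---|
| 0 | 1.0 | 1.0 | 1.0 |
| 0.1 | 0.59 (rate 0.29025/0.345 = 0.841) | 1.13 (rate 0.515) | 1.0 |
| 0.2 | 0.43 | 1.27 | 1.0 |
| 0.3 | 0.35 (rate 0.33075/0.435 = 0.760) | 1.44 (rate 0.576) | 1.0 |

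**Same check on the CPC scale.** Section 4.4 gives a mean CPC without treatment of 3.20. Assume shares 0.25 / 0.35 / 0.40 and mean CPC 4.9 (suppressed) and 3.6 (other). The continuous mean must then be (3.20 − 1.225 − 1.26) / 0.40 = 1.7875. Positive values are benefit, for f = 0.2 to 0.4:

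| Share of the class gap gained by those moved | True overall effect | Suppressed | Other | Continuous |
|---|---|---|---|---|
| all | 0.19 to 0.38 | 0.00 | 0.00 | 0.00 |
| half | 0.10 to 0.19 | 0.00 | −0.10 to −0.21 | −0.13 to −0.23 |
| none | 0.00 | 0.00 | −0.20 to −0.42 | −0.27 to −0.47 |

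With shares 0.15 / 0.45 / 0.40 (continuous mean 2.11) the pattern is the same: full gain gives 0.17 to 0.35 overall and 0.00 in each class; no gain gives −0.10 to −0.24 in other and −0.27 to −0.46 in continuous.

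Sorting by the class before treatment recovers the effect. At f = 0.4 with full gain and shares 0.25 / 0.35 / 0.40, it is 0.4 × 1.3 = 0.52 in suppressed, 0.4 × 1.8125 = 0.73 in other and 0 in continuous. Weighted, 0.25 × 0.52 + 0.35 × 0.725 = 0.38, the true overall benefit.

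**The case against.** The strongest reply is that the bias is conditional. It needs ghrelin to change the EEG class by 24 hours, which the protocol assumes and has not shown; section 6.3 says ghrelin has not been given to such patients. With f = 0 there is no bias. That stands, so the documents do not support saying outright that the subgroup results are biased. But the condition is the trial's own working hypothesis, and an analysis that fails when the hypothesis is right is poorly chosen.

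A reader might also infer that if ghrelin works through brain activity, the benefit must vanish in every subgroup. That needs the whole benefit to pass through moves between three coarse classes. Benefit within a class, benefit after 24 hours during the week of treatment, or benefit by another route would still show. The half-gain row does not give zeros.

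A reader might infer that a later phase 3 trial would enrol the wrong patients. Section 4.4 speaks of larger phase 3 trials if potential benefit is shown, but nowhere are the EEG subgroups made the basis for choosing their population.

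Section 9.2 does warn about subgroups, but about precision only. The prognostic value of the 24-hour pattern is a fair reason to want it; it does not make a reading taken after dosing a valid stratum for a randomised comparison. Nor is this a detail left to a statistical analysis plan, since section 9.2 itself fixes the time point.

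**Conclusion.** The point holds in conditional form. The 24-hour EEG follows the first dose by at least 9 to 12 hours, and background continuity appears in the protocol both as a response to ghrelin and as a basis for the subgroups. If ghrelin changes the class by then, the comparisons within classes and the heterogeneity assessment are biased. The timing and the dual role come straight from the text and are firm.

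The size is not firm. Class shares, outcome rates and the fraction moved are all assumed, and the odds ratios use a good/poor split although the primary analysis in section 9.1 uses the whole CPC scale. The figures show the direction of the bias and that it can be large; they do not predict its size in this trial.

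The scope is the secondary subgroup analysis. The single intention-to-treat comparison of CPC at six months is unaffected.

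**What to change.** In section 9.2, define the three subgroups by the last EEG epoch before the first study dose, or before randomisation, and fix which. Add a separate category for patients with no such EEG. Report the 24-hour pattern as a mechanistic outcome alongside the measures in section 7.1.3. If outcome by 24-hour pattern is still wanted, label it exploratory and non-randomised, and do not use it to judge heterogeneity of effect.

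The change needs no extra patients and no new procedure: admission EEG is listed as baseline data in section 7.3, and section 7.1.3 describes continuous EEG on days 0 to 3 as current care in all participating hospitals. It should not be assumed that every patient has a recording before the first dose. No section requires one, EEG is not an inclusion criterion, and the table of procedures has no EEG row. Hence the fallback category.

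The costs are real: some patients will lack an early EEG, the epochs will fall at varying times after the arrest, and an early pattern may carry less prognostic information than the one at 24 hours.
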